**COMRADE: Collaborative Care Management for Distress and Depression in
Rural Diabetes**

NCT02863523

December 11, 2017

PROTOCOL AND DATA ANALYSIS

1. Introduction

Type 2 diabetes (T2D), a significant public health burden, is more prevalent in the southeastern US which includes most of the CDC defined “Diabetes Belt” [1]. It is estimated that 9.3% of Americans have diabetes and in the counties included in the Diabetes Belt; the percent affected ranges from 11 to 11.7%. Those with T2D are twice as likely to have symptoms of depression and this relationship may be bi-directional [2]. Depressive symptoms may also interfere with glycemic control and adherence to the prescribed treatment regimen [3]. Diabetes related distress, originally investigated by Polonsky et al. [4], can be associated with depressive symptoms but appears to be a distinct condition [5]. Diabetes related distress reflects the emotional distress, defined as “patient concerns about disease management, support, emotional burden, and access to care”. High levels of regimen related distress have been associated with poor medication adherence, lower self-efficacy, and higher levels of HbA1c [6]. Early evidence suggests that improvement in depressive symptoms and/or distress have been associated with improvement in glycemic control and quality of life [7–9]. Katon et al. [7] described a shared or integrated approach to both T2D and depression using a care manager specifically trained in both diseases, with psychiatrist back-up. However, Katon et al.’s work was done in the northwestern US with a predominantly Caucasian population with diabetes and depression only (distress not targeted) with good access to medical care services and the availability of back-up psychiatrists. Bogner et al. [8] implemented an integrated care management strategy for patients with T2D and co-morbid depression who were likely to have medication adherence challenges. This study also provided excellent evidence for the present study; however, it was conducted in an urban setting in the northeastern US, targeted depressive symptoms only, and outcomes were only measured at 12 weeks so that the long-term effect of their model is unknown. Hessler et al. [9] used an electronic intervention model and showed that reductions in regimen-related distress were associated with improvements in medication adherence and glycemic control. However, this study was conducted in an urban location on the west coast. Despite the limitations of available data, the American Diabetes Association in its latest guidelines [10] now recommends both regular screening for psychosocial issues as well as evaluation and treatment including a collaborative patient-centered approach involving behavioral health professionals when indicated. However, the extent to which this collaborative behavioral and medical care model can be effectively implemented in busy primary care practices in the southeastern US diabetes belt or other areas of high prevalence, where many patients with poorly controlled T2D and behavioral co-morbidities are managed, remains poorly defined. The investigators undertook the present study to investigate the pragmatic implementation of an integrated care delivery model in the diabetes belt in the rural southeastern United States with a much larger African American population.

In this protocol, the authors describe the design, rationale, and methods from a prospective randomized pragmatic trial of an innovative model involving a culturally-relevant integrated medical and behavioral intervention for uncontrolled T2D, tailored to the unique needs of patients in the southeastern US diabetes belt. The objective of this clinical trial was to determine

the feasibility for delivering and evaluating coordinated and integrated behavioral and medical care for adult patients with uncontrolled T2D who have comorbid diabetes-related distress and/or depressive symptoms, in the context of a busy primary care practice and surrounding rural communities. The intervention included a carefully defined protocol for face-to-face and telephone delivered cognitive behavioral health interventions, tailored to the presence and severity of co-morbid distress and/or depression, in addition to routine medical care for T2D.

2.2. Intervention design

The study was designed as a prospective, randomized, non-blinded pragmatic trial with randomization at the patient level to the intervention arm or to usual care. For the intervention arm, a collaborative or integrated care model involving tailored cognitive-behavioral therapies plus American Diabetes Association guideline [10]-informed standard medical care was considered to represent the most practical approach to treating the established co-morbid illness in busy primary care settings in the southeastern US. The intervention was designed to utilize modified versions of evidence-based collaborative care management strategies – particularly those described by Katon et al. [7] and Banger et al. [8]. Further, the intervention model was built on the authors' prior work [11], and was designed to:

1. Involve an integrated and collaborative care delivery system that extends the capacity of busy primary care providers to be able to screen and manage the psychological and behavioral needs of complex co-morbid patients with T2D
2. Focus on specific behavioral problems such as depressive and diabetes-related distress symptoms that prior literature suggests limits optimal care outcomes
3. Utilize a unique stepped care approach that quickly moves the patient to the right level of care and increases or decreases the degree of intervention based on patient response
4. Be culturally tailored to be relevant in the southeastern US and to African Americans
5. Use a trained care manager linked to primary care clinicians and health psychologists so that it might be readily deployed even in communities without access to a psychiatrist
6. Employ a community health worker to provide specific social support and navigation
7. Use a combined face-to-face and telephone visit structure to improve care and cost efficiency and to facilitate generalizability in underserved and rural communities

2.3. Study population and setting

The study was specifically targeted at patients with uncontrolled T2D who also reported either depressive symptoms and/or symptoms of diabetes-related distress, as measured by previously validated instruments (see below). In our prior pilot work in this same region using the same instruments [11], 40% of patients screened positive for diabetes related distress and 21.5% reported elevated depressive symptoms. The study took place in an academic Family Medicine clinic setting that included a residency program located in the southeastern U.S.

2.3.1. Screening

The population screened for this study included: adult patients (18 to 75 years of age) who had established care at the academic primary care practice (at least one visit in the last 12 months) and who had an electronic medical record established diagnosis of T2D and a recent (< 12 mo.) HbA1c that reflected inadequate glycemic control ($\text{HbA1c} \geq 7.0$). Exclusion criteria for screening included a medical record established diagnosis of advanced disease (e.g., end stage renal disease, advanced heart failure, blindness, metastatic cancer) or the presence of alcoholism, cognitive impairment, or major psychiatric disease that would preclude active participation. Individuals who met preliminary eligibility were contacted by the study coordinator and invited to be seen for a study-specific visit or was screened following a regular provider visit. At the time of placement into an examination room for the study visit, a statement of informed consent and HIPPA consent was carefully reviewed with each potential participant. A two-item version of the Diabetes Distress Scale (DDS-2) and the two-item version of the Patient Health Questionnaire (PHQ-2) was then administered as a screening instrument by office staff. These 2-item versions have excellent sensitivity (95% and 97%, respectively), and are defined in greater detail below in the outcome measures section. Study staff collected the completed measures and scored them. If the score on either measure was considered positive (mean score > 3 on DDS-2; total score > 3 on PHQ-2), the individual was assessed regarding glycemic control. A screening fingerstick HbA1c test was obtained while the patient was in the examination room and evaluated using a Siemens analyzer [DCA Vantage portable analyzer, Siemens Medical Solutions, Malvern, PA] as described below. If the patient met all the screening criteria described above, had a HbA1c value that day that was > 7.0 , and also had positive co-morbid behavioral symptoms (depressive and/or diabetes-related distress symptoms on one or more of the 2 item screening instruments), then he/she was scheduled for an enrollment visit into the study. Once enrolled, the patient completed the full DDS-17 and PHQ-9 plus additional baseline instruments that are defined below and was then scheduled for a study orientation visit.

2.4. Sample size and randomization procedures

Sample size was estimated as follows. The primary outcome measure was determined to be the change in mean HbA1c from baseline to 12-months follow-up. In the intervention arm, mean HbA1c was hypothesized to decrease by -0.7 compared to no change in the usual care arm (based on values reported by Bogner et al. [8]). Using an $\alpha = 0.05$ and a power estimate of 0.80, the crude sample size needed in each group was approximately $n=50$ for a total sample size of $N=100$ patients. The investigators chose to recruit and randomize approximately 70 patients into each arm anticipating the possibility of dropouts and incomplete follow-up data in some patients. Randomization was designed as a blocked randomization process, controlled by one of the investigators, using a computer-generated allocation sequence with allocation concealment from treating providers, with eligible patients randomized in blocks of four to the intervention or control group. Patients were randomized at the beginning of the orientation visit, held one week after the screening visit) and were provided group specific orientation to the study as detailed below.

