2.5. Implementation

At the outset of the study, project faculty met weekly and hired a project coordinator who managed logistics and facilitated patient recruitment as well as all data collection and data entry.

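### Blocks of four, with concealment described only for treating providers, could make up to one third of allocations predictable to staff who know the block size and past assignments

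*Combined protocol and SAP*

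**What the plan says.** Section 2.4 gives the block structure: "with eligible patients randomized in blocks of four to the intervention or control group". On who runs the process, it says: "Randomization was designed as a blocked randomization process, controlled by one of the investigators". On who is kept from the sequence, its wording is: "using a computer-generated allocation sequence with allocation concealment from treating providers". Four is the only block size given, no strata are described, and treating providers are the only people named as kept from the sequence. No release mechanism, such as a central system or sealed envelopes, is described.

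The timing is in the same section: "Patients were randomized at the beginning of the orientation visit". That visit came a week after screening, and Section 2.5.2 confirms that consent was signed before it.

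Section 2.2 describes a "prospective, randomized, non-blinded pragmatic trial with randomization at the patient level". Section 2.3 gives one setting: "The study took place in an academic Family Medicine clinic setting". Section 2.5 describes "a project coordinator who managed logistics and facilitated patient recruitment as well as all data collection and data entry".

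Section 2.6.1 compares change in HbA1c between arms by t-test or ANOVA. Covariates are added only for baseline characteristics that differ significantly.

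**The concern.** Treating providers are not the only people who need to be kept from the next allocation. The coordinator contacts and invites patients, manages logistics and collects the data. In an open trial at one clinic, a person in that role could plausibly observe who went to which arm. If that person also knew the block size, some upcoming allocations would follow by elimination.

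Consent comes first, which closes most of the usual route. What remains is the week between consent and the orientation visit. The order of visits, rescheduling and the pursuit of no-shows settle which patient takes the next slot. If a known slot influenced those decisions, the arms could differ in severity or motivation. A t-test on change would not correct that, and a covariate rule triggered by significance would miss any imbalance short of significance.

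**Working it through.** The documents give no predictability figure to reproduce, so the calculation starts from the design facts.

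**Inputs.**
- Block size 4 (Section 2.4).
- Two per arm in each block, inferred from the equal targets: "recruit and randomize approximately 70 patients into each arm".
- Total 2 × 70 = 140, so 140 / 4 = 35 blocks.
- Assumptions: a single running sequence, and an observer who knows the block size, the block boundaries and every completed allocation in order. The documents state none of these.

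**Certain allocations just before randomization.** A 2:2 block has 6 orderings, hence 6 × 4 = 24 positions. Position 4 is always determined (6 of 6). Position 3 is determined only when the first two are equal (AABB and BBAA, 2 of 6). Positions 1 and 2 never are. The total is 6 + 2 = 8 of 24 = 33.3%, and 140 × 1/3 = 46.7.

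**Best guess.** The chance of guessing right at positions 1 to 4 is 1/2, 2/3, 2/3 and 1. The mean is (1/2 + 2/3 + 2/3 + 1) / 4 = 17/24 = 70.8%, against 50% by chance.

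**Effect of patients still waiting ahead.** At consent, earlier patients may not yet have been randomized, so the observer's knowledge stops short of the slot just before.

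| Patients pending ahead | Chance of certainty, positions 1 to 4 | Certain share | Of 140 | Best guess |
|---|---|---|---|---|
| 0 | 0, 0, 1/3, 1 | 33.3% | 46.7 | 70.8% |
| 1 | 0, 0, 0, 1/3 | 8.3% | 11.7 | 58.3% |
| 2 | 0, 0, 0, 0 | 0% | 0 | 54.2% |
| 3 | 0, 0, 0, 0 | 0% | 0 | 50.0% |

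With one pending, only position 4 after two equal allocations is certain: (1/3) / 4 = 8.3%.

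**Varied block sizes.** Sequences of 140 were simulated 1,000 times, with an observer who knows the possible sizes and the full history. Sizes 4 and 6 at random give about 5.5% certain and a best guess of about 69%. Sizes 4, 6 and 8 give about 2.3% certain (140 × 0.023, about 3) and about 68%. Varying the block size removes certainty but hardly changes the best guess.

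**What a baseline check can show.** Of the 8 determined positions, 4 fall in each arm. Suppose, for illustration, that patients steered to known intervention slots are 0.5 SD better and those steered to known control slots 0.5 SD worse. The arms then differ at baseline by (1/3)(0.5) − (1/3)(−0.5) = 0.33 SD. Predictable slots pooled across arms average (0.5 − 0.5) / 2 = 0, the same as the other slots, so a pooled comparison sees nothing.

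Comparing slots predictable as intervention with slots predictable as control does see it, but each group has only about 46.7 / 2 = 23 patients. The standard error is √(2/23.3) = 0.29 SD. The difference detectable with 80% power at two-sided 5% is about (1.96 + 0.84) × 0.293 = 0.82 SD. The check is therefore low-powered.

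**The case against.** A reader might infer that recruiting staff knew a third of allocations in advance. The documents do not support that. They place the sequence with one investigator, and nothing says that the coordinator held the list, knew the block size, tracked allocations in order or performed randomization. That the coordinator saw past allocations is a reasonable inference from the role in an open trial, not a stated fact. This objection stands, and it makes one third an upper bound.

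Eligibility rests on numeric cut-offs and was settled, with consent, about a week before randomization. This also stands for steering at consent: one pending patient cuts the certain share to 8.3%, and two or more remove it. It does not close the later window, when visits are ordered or rescheduled. No recruitment rate is given, so the usual number pending is unknown.

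The covariate rule in Section 2.6.1 is a partial safeguard, but it acts only on significant differences. Baseline adjustment of any kind leaves unmeasured motivation uncorrected. The openness of self-reported outcomes to bias is mainly a matter of unblinded measurement, which block size does not change.

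Section 2.4 is written largely in the past tense, so a new allocation list may no longer be possible. That affects which remedy applies.

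**Conclusion.** The point holds as a gap in the described concealment. As written, the design could make up to 33.3% of allocations (about 47 of 140) certain in advance, with a best guess right 70.8% of the time. This requires someone who knows the block size and all past assignments, at the moment just before randomization. The figures assume 2:2 blocks and one unstratified sequence. With one patient pending the certain share is 8.3% (about 12 of 140), and with two or more it is zero.

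It would be wrong to read this as evidence that allocation was subverted or that the arms are biased. The documents show neither, and the counts measure opportunity rather than bias in HbA1c change. Only the sponsor can say whether concealment reached beyond treating providers. The point is worth acting on because the remedies cost little and improve the analysis even if nothing went wrong.

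**What to change.** **If randomization is still open.** Draw block sizes at random, for example from 4, 6 and 8, and do not disclose them. Keep the list and the sizes from the coordinator and from anyone else who recruits or collects data. Release one allocation at a time, only after the patient has arrived and all baseline measures are complete. Concealment matters more than the change of block size, because the best guess falls only from about 71% to about 68%.

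**In either case, reconcile the timing of baseline.** Section 2.3.1 has the full PHQ-9 and DDS-17 completed at enrollment, before the orientation visit. Section 2.5.3 has the full battery completed after randomization at that visit.

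**If randomization is finished.**
- State who could see the list and the block size, and how each assignment was released.
- Adjust the primary HbA1c comparison for baseline HbA1c whatever the baseline tests show, in place of the significance-triggered rule.
- Add PHQ-9 and DDS-17 as covariates only if they were collected before allocation. Otherwise use the screening PHQ-2 and DDS-2.
- If a baseline check is run, compare slots predictable as intervention with slots predictable as control, and label it low-powered. Do not pool predictable slots against the rest.

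**Cost.** Final arm sizes may differ by a few patients if block sizes vary, and there is minor extra analysis work. No additional patients are needed.

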2.5. Implementation

At the outset of the study, project faculty met weekly and hired a project coordinator who managed logistics and facilitated patient recruitment as well as all data collection and data entry.

2.5.1. Intervention staff selection and training

The primary intervention was delivered by a team of behavioral providers working together including a nurse care manager who provided small-changes lifestyle coaching [11], a doctoral student in clinical psychology or psychologist who provided cognitive behavioral treatment sessions including elements of problem-solving therapy where indicated, and a community health worker who provided navigation and social support. The nurse care manager was an African American registered nurse from the local area with >10 years' experience in care management for patients with diabetes. A local African American adult female community health worker with >10 years' experience in chronic disease care, was hired to provide social support and navigation in the community to acquire needed diabetes resources. All staff hired had strong interpersonal skills including a demonstrated ability to establish rapport quickly with a wide range of people. The nurse manager and other intervention staff received extensive (≥ 80 h) training by the investigators in all aspects of the intervention including diabetes-specific evaluation and management, depression and distress specific evaluation and management, cognitive-behavioral/problem solving therapy intervention components, disease and severity stratification, response evaluation and stepped-care transitions, psychological and medical treatment intensification, working with providers and community partners, and project-specific evaluation. One of the investigators provided regular supervision of the care manager from a behavioral intervention perspective.

2.5.2. Orientation session

Patients who completed the screening visit and signed informed consent completed a study orientation visit one week later during which height, weight, and sitting blood pressure (BP) were measured using standardized procedures. All patients in both study arms were provided with educational materials about T2D (Living with Diabetes, American College of Physicians, Product #: 11033420E). Patients randomized at the orientation visit into the Usual Care Arm were provided with general information about the COMRADE study and with a brief orientation to future study assessment visits. Patients randomized to the intervention group were provided with general information about the COMRADE study, a weight scale, and were assigned to one of two levels of behavioral treatment based on the level of baseline scores (see below). Intervention group patients also received an innovative, patient-friendly Tracking for Success Calendar developed for daily monitoring of six possible diabetes and mood self-management behaviors including fasting blood glucose, weight, medication administration, food intake, step count, and mood. Each intervention arm patient was instructed to use this for the duration of the study and these records were reviewed at the start of every study-related session by the assigned behavioral interventionist. Following explanation of study materials and orientation to the COMRADE program, patients were scheduled to attend their first behavioral treatment session.

2.5.3. Initial assessment of co-morbid behavioral symptoms and severity stratification

Once randomized at the orientation visit, patients in both groups completed a full battery of measures which are detailed below. The full psychological measures [Patient Health Questionnaire-9 (PHQ-9) for depressive symptoms and the Diabetes-related Distress-17 (DDS-17) scales for diabetes-related distress symptoms], were promptly scored by study staff and used to triage or stratify patients into one of two appropriate evidence-based behavioral interventions based on the severity of symptoms of depression or distress [(Small Changes Lifestyle Coaching if PHQ-9 < 10 and/or mean DDS-17 < 3) or Cognitive Behavioral Therapy (CBT; PHQ-9 \geq 10 and/or mean DDS-17 – \geq 3.0)]. Based on these two measures, it was possible to have patients with only depressive symptoms, only diabetes-related distress symptoms, or a combination of both distress and depressive symptoms. This complex design was specifically chosen for pragmatic reasons related to: 1) insuring generalizability in primary care where patients with uncontrolled diabetes frequently have either or both of these co-morbidities, and 2) to explore whether evidence-based but tailored treatments would relieve varying levels of symptoms of diabetes-related distress and/or depression and facilitate diabetes control when delivered in this integrated care fashion in the context of a busy primary care practice. The proposed stratification design may also have the potential to be more efficient and cost-effective than providing a potentially suboptimal level of intervention for a period of time before intensifying treatment as might occur in a standard stepped care model. Therefore, the behavioral intervention was designed to pilot test a severity-stratified behavioral treatment model with patients being triaged at baseline to one of three levels of behavioral intervention (small changes lifestyle coaching, or one of two levels of cognitive behavioral therapy), each paired with guideline informed standard medical care delivered by the patient's primary care provider with available consultative support from the study's diabetologist to assist with medication selection and monitoring. All three levels of behavioral health intervention had the overarching goal of improving the patient's glycemic control (i.e., HbA1c) as well as improving depressive and/or distress symptoms.

